6.2.2 Severity

The NCI-CTCAE v 4.03 will be used to describe the event and to assess the severity of AEs. For AEs not adequately addressed in the NCI-CTCAE version 4.03, [Table 6](#) should be used.

Table 6: Toxicity Grading for AEs Not Covered in NCI-CTCAE (Version 4.03)

Severity	Description
GRADE 1	Mild; asymptomatic or mild symptoms; clinical or diagnostic observations only; intervention not indicated
GRADE 2	Moderate; minimal, local or noninvasive intervention indicated; limiting age-appropriate instrumental activities of ADL*
GRADE 3	Severe; medically significant but not immediately life threatening; hospitalization or prolongation of hospitalization indicated; disabling; limiting self-care ADL**
GRADE 4	Life-threatening consequences; urgent intervention indicated
GRADE 5	Death related to AE

Abbreviations: ADL = activities of daily living. Semi-colon indicates "or" within the description

* Instrumental ADL refer to preparing meals, shopping for groceries or clothes, using the telephone, managing money, etc.

**Self-care ADL refer to bathing, dressing and undressing, feeding self, using the toilet, taking medications, and not bedridden

Abnormal laboratory findings should be reported as AEs only if they are clinically relevant (see [Section 6.3.6](#)).

AE will be reported at the highest grade experienced. AEs which completely resolve and then recur will be recorded as a new AE.

6.3 Collection and Reporting

6.3.1 General AE Reporting

All AEs will be collected from the time the subject receives any investigational product through 30 days after receiving the last dose of investigational product, death, or initiation of new anticancer therapy, whichever occurs first. SAEs and AEs with potential immunologic etiology will be recorded up to 100 days and pregnancies up to 120 days after the last dose of investigational product, death, or initiation of new anticancer therapy, whichever occurs first.

Events that occur after the subject signs the informed consent but prior to the first dose of investigational product will be recorded as past medical history; events that start after the first dose of investigational product will be recorded as AEs. In addition, the Investigator should report any AEs that may occur after this time period which are assessed to have a reasonable possibility of being associated with investigational products.

All AEs must be promptly documented on the AE eCRF. The minimum information required for each AE includes event, duration (start and end dates), start time (for events occurring within 48 hours after the start of APX005M infusion) severity, seriousness, causality to investigational product, action taken, and outcome. Whenever possible, reporting specific diagnosis is preferred when reporting AEs in the AE eCRF rather than reporting individual signs and symptoms except for infusion related reactions and cytokine release syndrome.

All AEs that are considered related to investigational products must be followed to resolution, stabilization, until improvement is not expected, 30 days after receiving the last dose of investigational product, death, or initiation of new anticancer therapy, whichever occurs first. SSAR will be followed until resolution, stabilization, or until resolution is not anticipated.

If an office visit is not possible, a follow-up of ongoing AEs should be attempted by telephone and documented in the subject's source file. AEs continuing at 30 days after the last dose of investigational product should have a comment in the source file by the Investigator that the event has stabilized or is not expected to improve.

The Investigator is responsible for evaluating all AEs, obtaining supporting source documents, and determining that documentation of the event is adequate. The Investigator may delegate these duties to subinvestigators and must ensure that these subinvestigators are qualified to perform these duties under the supervision of the Investigator and that they are listed on the FDA Form 1572.

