7. Women of childbearing potential (WOCBP) must have a negative serum pregnancy test within the 7 days prior to first dose of investigational product and a negative urine pregnancy test within the 3 days prior to first dose of investigational product, or a negative serum pregnancy test within the 3 days prior to first dose of investigational product
8. WOCBP must agree to follow instructions for method(s) of contraception for the duration of study treatment and 5 months after the last dose of investigational product. Males who are sexually active with WOCBP must agree to follow instructions for method(s) of contraception for the duration of study treatment and 7 months after the last dose of investigational product
9. Available archived or fresh tumor tissue sample for PD-L1 and other biomarker analysis
10. For subjects that consent to collection of tumor biopsies at study entry and before the first scheduled tumor assessment, primary or metastatic tumor that can be safely biopsied. A minimum of 24 subjects (6 subjects with each cohort/group) must consent to fresh core biopsies.

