5.2.4 Follow-Up

Follow-up period begins after the EOT visit. For subjects who discontinue treatment without documented PD, every effort should be made to continue monitoring their disease status by tumor imaging using the same schedule used while on treatment.

Subjects should be contacted approximately every 1 month for the first 3 months and every 3 months thereafter to:

- Collect information on subsequent therapy and response, if possible
- Record the time of documented PD for subjects who discontinue treatment without documented PD and cannot have regular tumor assessments.
- Collect information on SAEs, AEs with potential immunologic etiology and pregnancies.

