6.4 Pregnancy

Subjects will be instructed to notify the Investigator as soon as possible after becoming pregnant or learning of the pregnancy of a partner. If a subject or partner of a subject becomes pregnant during treatment or up to 120 days following the last study drug administration, the Investigator will notify Apexigen (or designee) within 24 hours of learning of the pregnancy.

If the subject becomes pregnant while receiving investigational product, the investigational product will be permanently discontinued. Exceptions to the investigational product discontinuation may be considered for life-threatening conditions only after consultation with the sponsor. The Investigator will discuss the risks and concerns of investigational drug exposure to a developing fetus and counsel the subject and/or pregnant partner (or ensure that such counseling is provided).

Pregnancies will be followed through the outcome of the pregnancy. Newborns should be followed for a minimum of 8 weeks.

The Investigator will complete a Pregnancy Surveillance Form and report the information regarding the pregnancy, outcome, and status of the newborn, as appropriate.

Protocol-required procedures for study discontinuation and follow-up must be performed on the subject unless contraindicated by pregnancy. Other appropriate pregnancy follow-up procedures should be considered if indicated.

7. Statistics

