8.2 Data Collection and Handling

8.2.1 Case Report Forms

As part of the responsibilities assumed by participating in the study, the Investigator agrees to maintain adequate case histories for the subjects treated as part of the research under this protocol. The Investigator agrees to maintain accurate eCRFs and source documentation as part of the case histories. These source documents may include subject diaries, laboratory reports, and other documents. Apexigen (or designee) will supply the eCRF, which will be completed in English.

Data collection will involve the use of the EDC system, to which only authorized personnel will have access.

The Investigator or designee must enter all results collected during the clinical study into eCRFs. Guidelines for completion of eCRFs will be reviewed with study site personnel at the site initiation visits. Investigators are responsible for approval of the entered/corrected data. Detailed instructions may be found in the other study-specific documents.

All entries made on the eCRF must be verifiable against source documents. In addition to periodic monitoring occurring within the system by study monitors, programmatic edit checks and data listings will be used to review the data for completeness, logic, and adherence to study protocol. As a result of this monitoring and these checks and queries may be electronically issued to the clinical study sites and electronically resolved by those sites.

All data collected in the context of this study will be stored and evaluated per regulatory requirements and applicable guidance for electronic records. Also, data will be stored and evaluated in such a way as to assure subject confidentiality in accordance with the legal and regulatory requirements applying to protected health information. Study records (e.g., copies of eCRFs and regulatory documents) will be retained at the study site, along with adequate source documentation. The study file and all source data should be retained for the time period required by applicable regulatory requirements and will not be destroyed until written notification is given by Apexigen (or designee) for destruction.

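### Pregnancy recording and 24-hour sponsor notification stop 120 days after the last dose, but the protocol requires contraception for 5 months (women) and 7 months (men)

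*Protocol*

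**What the plan says.** **Contraception.** Inclusion criterion 8 (Protocol 2.2.1.1, also in the synopsis) has women of childbearing potential use contraception "for the duration of study treatment and 5 months after the last dose of investigational product". For men who are sexually active with such women, the period is "study treatment and 7 months after the last dose of investigational product".

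**Recording.** Protocol 6.3.1 collects "pregnancies up to 120 days after the last dose of investigational product, death, or initiation of new anticancer therapy, whichever occurs first". SAP 5.4.3 repeats this wording.

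**Notification.** Protocol 6.4 requires the investigator to tell the sponsor within 24 hours of learning that a subject or a subject's partner "becomes pregnant during treatment or up to 120 days following the last study drug administration". It has no cut-off at new anticancer therapy.

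**Provisions with no end date.**
- Section 6.4 opens by having subjects told to inform the investigator promptly of their own or a partner's pregnancy.
- Section 6.4 also says "Pregnancies will be followed through the outcome of the pregnancy" and "The Investigator will complete a Pregnancy Surveillance Form and report the information regarding the pregnancy".
- Section 5.2.4 says "Subjects should be contacted approximately every 1 month for the first 3 months and every 3 months thereafter" and lists pregnancies among the items to collect.
- Section 8.2.1 says "The Investigator or designee must enter all results collected during the clinical study into eCRFs".

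**The concern.** By setting 5-month and 7-month contraception periods, the protocol treats conception in that time as something to prevent. One would expect a pregnancy in the same period to be recorded and reported promptly, yet the dated duties end at 120 days. A site that follows 6.4 to the letter could be told of a partner's pregnancy in month 6 and owe the sponsor no 24-hour notice. Whether that pregnancy is recorded and followed would depend on how the site reads the undated sentences.

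What is at stake is the safety information on exposed pregnancies, for female subjects and for partners of male subjects.

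A second, smaller question is why 6.3.1 and 6.4 end on different terms when a subject starts new anticancer therapy.

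**Working it through.** There is no power or alpha figure to reproduce. The check compares the stated windows and converts months to days.

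**Inputs**
- Recording window: 120 days after the last dose, or earlier at death or new anticancer therapy (Protocol 6.3.1, SAP 5.4.3).
- Notification window: 120 days after the last dose (Protocol 6.4).
- Contraception after the last dose: 5 months for women, 7 months for men (inclusion criterion 8).

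**Conversion**
- 5 months = 150 to 153 days (30-day months give 150; calendar months give 150-153).
- 7 months = 210 to 215 days (30-day months give 210; calendar months give 212-215).

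**Days outside the windows = contraception period minus 120**

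| | Contraception period (days) | Covered (days) | Outside (days) | Share outside |
|---|---|---|---|---|
| Female subjects | 150-153 | 120 | 30-33 | 30/150 = 20% to 33/153 = 22% |
| Partners of male subjects | 210-215 | 120 | 90-95 | 90/210 = 43% to 95/215 = 44% |

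**Do the undated provisions close the gap?**
- The subject's duty to inform the investigator (6.4) and the follow-up contacts (5.2.4) both let the investigator learn of a later pregnancy. Neither gives a deadline for telling the sponsor or changes the recording window.
- The sentences on outcome follow-up and the Pregnancy Surveillance Form (6.4) can be read as covering every pregnancy, or only those in the 120-day window defined just before them.
- The data-entry rule in 8.2.1 covers results that are collected. It does not say which pregnancies must be collected.
- The sentence in 6.3.1 on events after the window concerns AEs judged possibly associated with the investigational products. It does not mention pregnancy.

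**New anticancer therapy.** Take a subject who starts new therapy at day 60 and becomes pregnant at day 80. Under 6.3.1 and SAP 5.4.3 recording has already stopped. Under 6.4 the investigator must still notify the sponsor within 24 hours, because day 80 is before day 120. The two sections disagree on recording, but the notification duty holds.

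**The case against.** The strongest reply is that nothing in the documents says the reporting window must equal the contraception period. The sponsor chose 120 days, and aligning the two is a reviewer's judgement. That is fair, and it keeps the severity low. It does not explain why the protocol sets no prompt reporting duty for part of a period in which it asks subjects to avoid conception.

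The second reply is that such pregnancies would come to light anyway. This stands in part. Subjects are told to report a pregnancy with no end date, and follow-up contacts ask about it. A reader might infer that pregnancies after day 120 go unseen; the documents do not support that. The gap is in the duty to record and to notify promptly. The contacts also miss some subjects: under 4.2, those who stop treatment because they start another anticancer therapy do not enter follow-up.

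Three other stronger readings should be set aside.
- **That the contact schedule skips the women's gap.** This holds only if the end-of-treatment (EOT) visit is near day 21. The third monthly contact comes about 91 days after that visit, so an EOT visit between about days 29 and 62 puts it at days 120-153, inside the gap. Section 5.2.3 allows the visit to be later, and the contact intervals are only approximate.
- **That birth defects would be missed because of the 120-day limit.** A full-term birth after conception on the last dosing day would also fall beyond the 100-day SAE window, so this is not specific to the gap. Section 6.3.1 also gives a route for later events judged possibly associated.
- **That the new-therapy cut-off loses notifications.** Section 6.4 has no such cut-off.

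**Conclusion.** The mismatch is real and minor. The explicit recording and 24-hour notification windows end about 30-33 days before the women's contraception period does and about 90-95 days before the men's. The separate cut-off at new anticancer therapy in 6.3.1 and SAP 5.4.3 is a recording inconsistency only.

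The day counts depend only on how months are converted and are not a risk estimate, since the documents give no pregnancy rate. The comparison rests on inclusion criterion 8. The Europe-only contraception appendix was not in the text available for review, and the point does not depend on it. Efficacy, DLT decisions and sample size are not affected. The change is worth making because it supports participant and partner safety and needs only wording.

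**What to change.** 1. In Protocol 6.3.1 and 6.4, and in the restatement in SAP 5.4.3, extend pregnancy recording and, where stated, 24-hour notification to at least 5 months after the last dose for female subjects and 7 months for partners of male subjects. Apply this to any pregnancy the investigator learns of.
2. Remove the new-anticancer-therapy cut-off for pregnancies from 6.3.1 and SAP 5.4.3, so that they agree with 6.4.
3. State in 6.4 that follow-up to outcome and the Pregnancy Surveillance Form apply to every pregnancy in these windows.

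**Cost.** The change is wording in two protocol sections and one SAP paragraph, plus a few more reports. No visits are added, because the duty covers only pregnancies the investigator learns of. Protocol 8.1.2 requires IRB/IEC approval before an amendment is implemented, so it is best bundled with another amendment.

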3.1 Subject Enrollment and Treatment Administration

All subjects who sign a consent form will be assigned a unique Subject Identification Number. This number will be used to identify the subject throughout the study and must be used on all study documentation. Subjects will be considered enrolled after receiving any investigational product; consented subjects who do not receive investigational product will be considered screen failures.

The Apexigen Medical Monitor (or designee) will review the subject's information before enrollment. Only subjects who are approved by the Apexigen Medical Monitor (or designee) will be allowed to enroll in the study. During normal business days, a minimum of 24 hours will be required for the Apexigen Medical Monitor (or designee) to approve a subject for enrollment. Additional time may be required when approval is sought during a weekend or holiday.

Subject enrollment into a DL cohort of the Phase 1b dose-escalation or in the Phase 2 dose-expansion will follow the rules outlined in [Section 2.2](#).

On treatment days, nivolumab will be administered first, followed by APX005M.

During Phase 1b dose-escalation, in any of the multi-subject cohorts, the first two subjects must receive the first dose of investigational product at least 72 hours apart.

During the Phase 1b dose-escalation portion of the study all subjects will be monitored in the research clinic for 4 hours after the first 2 infusions of APX005M and as clinically indicated thereafter and during the Phase 2 dose-expansion portion of the study.

All subjects will be discharged from clinic after a clinical evaluation. Subjects should have stable vital signs including: lack of orthostatic hypotension (systolic blood pressure >100 mmHg, or no lower than 10 mm from baseline) without IV hydration (no hydration for at least 2 hours prior to discharge), lack of hypoxia (oxygen saturation >90% without oxygen), temperature <38°C, heart rate <110 beats/min.

After discharge, all subjects in Phase 1b should be monitored by a caregiver or by a healthcare professional for 24 hours after the first 2 infusions of APX005M and as clinically indicated thereafter. Subjects in the Phase 2 dose-expansion portion of the study should be monitored as clinically indicated.

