6.3.5 Non-serious AEs

The collection of AE information begins after subject's written consent to participate in the study: AEs that occur after consent, but prior to the first dose should be recorded as Medical History. If an ongoing AE changes in its intensity or in its perceived relationship to investigational product, a new AE entry for the event should be completed. AEs should be followed to resolution, stabilization, a minimum of 30 days after the discontinuation of the investigational product, or reported as SAEs if they become serious.

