5.4.3.3 Adverse Events

All AEs will be collected in the eCRF from the time the participant signs informed consent through 30 days after the last dose of investigational product, death, or initiation of new anticancer therapy, whichever occurs first. AEs will be coded to system organ (SOC) and preferred term (PT) using the MedDRA dictionary v18.0.

The NCI-CTCAE will be used to assess the severity of AEs.

The relationship of each AE to the investigational product will be classified as related or unrelated. If relationship is missing, the event will be listed as missing relationship but summarized as related.

Summaries will focus on the TEAEs. They will be summarized by dose level and overall for Phase 1b and by cohort and overall for Phase 2 (including participants treated at RP2D in Phase 1b). The following summary tables will be provided:

- An overall summary of the frequency of participants reporting all TEAEs, serious TEAEs, TEAEs with CTCAE grade 3 or higher, treatment-related TEAEs (separately for APX005M and nivolumab), and TEAEs leading to treatment discontinuation (separately for APX005M and nivolumab), TEAEs with fatal outcome.
- TEAEs by SOC and PT
- Serious TEAEs by SOC and PT
- TEAEs with CTCAE grade 3 or higher by SOC and PT
- Treatment-related TEAEs by SOC and PT (separately for APX005M and nivolumab)
- TEAEs leading to treatment discontinuation by SOC and PT (separately for APX005M and nivolumab)
- TEAEs with fatal outcome by SOC and PT
- TEAEs by SOC and PT, and by maximum CTCAE grade

All AEs will be listed by dose level (Phase 1b)/cohort (Phase 2, including participants treated at RP2D in Phase 1b), and then study site, participant number, and cycle day. Separate listings will be produced for TEAEs, serious TEAEs, TEAEs leading to APX005M discontinuation, delay, and interruption, and TEAEs with fatal outcome. Separate listings will be generated for immune-mediated events.

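### A serious complication of a pre-dose study biopsy has no required route to SAE reporting, and the documents give two start points for AE collection

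*Protocol*

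**What the plan says.** **When AE collection starts.** Protocol 6.3.1: "All AEs will be collected from the time the subject receives any investigational product". Protocol 6.3.5: "The collection of AE information begins after subject's written consent to participate in the study". SAP 5.4.3.3: "All AEs will be collected in the eCRF from the time the participant signs informed consent".

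**What happens to events between consent and first dose.** Under Protocol 6.3.1, events after consent but "prior to the first dose of investigational product will be recorded as past medical history". Protocol 6.3.5 agrees: "AEs that occur after consent, but prior to the first dose should be recorded as Medical History". SAP 5.4.3 gives the same rule. It then concludes that whatever is on the AE eCRF pages is a TEAE.

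**What is done to subjects in that window.** Protocol 5.2.1 and the biopsy footnotes to both schedules in 5.1 place a core biopsy before first dose in subjects who agree to it. Inclusion criterion 10 sets a floor: "A minimum of 24 subjects (6 subjects with each cohort/group) must consent to fresh core biopsies".

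**Who is left out of the safety tables.** Protocol 3.1: "consented subjects who do not receive investigational product will be considered screen failures". SAP 3.2 limits the safety population to those who received both products. SAP 5.4.1.3 puts medical history in a listing and in no summary table.

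**The concern.** The baseline core biopsy is an invasive procedure done for the study, after consent and before any drug. The plan files everything that happens in that interval as history. It makes no exception for an event that is serious and was caused by the study procedure. Nothing then obliges a site to tell the sponsor within 24 hours that a subject was, for example, hospitalised by the biopsy, while further subjects are being asked to agree to the same procedure.

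There is also an analysis problem. Safety is a secondary objective, and the documents disagree on when AE collection begins. Two sites reading them in good faith could put the same pre-dose event on different eCRF pages, and the SAP lets the page decide whether the event counts as treatment-emergent.

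**Working it through.** The plan has no figure to reproduce, so the check is a comparison of texts.

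**1. Is there a required SAE route for a serious pre-dose biopsy complication?**
- Protocol 6.1.1 defines an AE through use of a drug, and 6.1.4 builds SAEs from AEs. A biopsy complication before any drug does not clearly qualify.
- Protocol 6.3.1 opens the collection window at first product. Its only extension is forward in time, to later events thought to be associated with the products.
- The required AE fields include "severity, seriousness, causality to investigational product, action taken, and outcome". Causality is to product only, and relation to a study procedure is not among the minimum items.
- Protocol 6.3.3 asks for 24-hour notice of any SAE or serious suspected adverse reaction. It gives no start date and does not mention procedures. It therefore neither excludes a pre-dose report nor clearly overrides the medical-history rule.

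Result: a report is possible, but no text requires it.

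**2. Is the window actually used for a study procedure?** Yes. The floor is 4 cohorts/groups × 6 = 24 consenting subjects. The biopsies are paired. The second is taken during Cycle 3 (Protocol 5.2.2 and 5.6.5), so its complications fall inside AE collection. The gap concerns the baseline biopsy only.

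**3. Where does the event end up?**
- Subject later receives both products: medical history, listing only.
- Subject never dosed: screen failure, outside the safety population.

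**4. Do the start points agree?**

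| Place | Collection starts | Pre-dose events go to |
|---|---|---|
| Protocol 6.3.1 | first product | medical history |
| Protocol 6.3.5 | written consent | medical history |
| SAP 5.4.3 | after first dose, for AE pages | medical history |
| SAP 5.4.3.3 | informed consent | not stated |

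**5. Does the disagreement reach a table?** SAP 5.4.3 first defines a TEAE by occurrence or worsening after first dose. It then treats every AE-page entry as a TEAE. That shortcut is valid only while no pre-dose event is on those pages. If a site follows SAP 5.4.3.3 and enters one there, and the subject goes on to receive both products, the event enters the TEAE summaries despite its earlier onset. If the site also leaves causality blank because no product had been given, SAP 5.4.3.3 summarises the event as related.

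**The case against.** The strongest reply is that starting AE collection at first dose is a deliberate choice, stated three times, and that other routes exist. Protocol 6.3.3 covers any SAE without a start date and points investigators to the applicable reporting rules. Protocol 8.1.1 and 8.1.2 invoke GCP and IRB/IEC reporting. The sponsor's Medical Monitor reviews each subject before enrollment (3.1) and might see a recorded complication. The biopsies are optional, and archived tissue is accepted for baseline. On the SAP, collecting from consent and filing pre-dose events as history can be read together, as Protocol 6.3.5 does, and the onset-based TEAE definition is already there.

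Much of this stands, and it rules out several stronger readings that a reader might infer:
- *Such events are never reported, or the sponsor could not learn of them.* The text does not say so. A report is allowed, and pre-enrollment review and the listings could reveal the event. What is missing is the requirement.
- *Only the failure reason is kept for a screen failure.* SAP 3.1 lists screen failures including the reason, and SAP 5.4 puts everyone entered in the database into listings.
- *The enrollment-suspension rules are blinded by this gap.* Their triggers are Grade 5 suspected adverse reactions, Grade 4 infusion reaction/cytokine release, and Grade 3 or higher immune-related AEs. A biopsy complication would generally not trigger them even if reported.

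Optional consent does not remove the need for a reporting rule once the procedure is done. Nor does a plausible joint reading of the SAP repair the page-based TEAE sentence.

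**Conclusion.** The point holds in two parts. First, a serious complication of the baseline study biopsy has no required route to 24-hour SAE reporting. Second, the AE start point is inconsistent across Protocol 6.3.1, Protocol 6.3.5 and SAP 5.4.3.3, and the page-based rule in SAP 5.4.3 could turn a pre-dose event into a TEAE.

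At least 24 subjects are to consent to these biopsies. The documents give no complication rate, so the number of events affected is not estimated. The TEAE miscount is conditional on a site entering a pre-dose event on the AE pages for a subject who then receives both products. No efficacy estimate, sample size or decision rule depends on this. It should be changed because it is a subject-protection gap that is cheap to close.

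**What to change.** **Protocol 6.3.1, 6.3.3 and 6.3.5.** State that from ICF signature to first dose, any SAE related to a procedure done under the protocol, optional biopsies included, is recorded on the AE eCRF and reported within 24 hours. Say that this applies to screen failures and holds despite the drug-based definition in 6.1.1. Provide a place to record relation to the procedure. Other pre-dose events stay as medical history.

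**SAP 5.4.3 and 5.4.3.3.** Use the same single start rule. Keep the TEAE definition based on onset or worsening after first dose, and delete the sentence that makes every AE-page entry a TEAE. That deletion becomes necessary once pre-dose events can be on those pages. List pre-dose procedure-related events separately, screen failures included.

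**Cost.** A few sentences, a field for relation to the procedure, one listing and a few extra SAE reports. No dose, eligibility criterion or sample size changes.

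**Timing.** The SAP's table shells are dated February 2021, after the estimated last enrollment of May 2020. If enrollment had closed by then, the protocol edit would come too late for baseline biopsies already taken. The SAP correction and the listing would still be useful, with a check of medical-history and screen-failure records for such events.
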